Official Title: Role of Levothyroxine Supplementation in Delayed Recovery Following Cardiac Surgery

NCT Number: NCT06660823

Document Date: November 1, 2024

Protocol Of A Paper For Partial Fulfilment Of Research In Anesthesia, ICU and pain management

The title: Role of Levothyroxine supplementation in delayed recovery following cardiac surgery.

NAME OF RESEARCHER: [name]

Academic Position: lecturer of Anaesthesia, Intensive Care and Pain management

Department: Faculty of Medicine-Ain Shams University

NAME OF RESEARCHER: [name]

Academic Position: Lecturer of Anaesthesia, Intensive Care and Pain management

Department: Faculty of Medicine-Ain Shams University

**Faculty of Medicine
Ain Shams University
2024**

1. INTRODUCTION/ REVIEW (Maximum 1000 words) *“References are needed”*

Research indicates that hypothyroidism decreases heart contractility, reduces stroke volume and rate, affects the vascular endothelium, and increases the risk of atherosclerosis, systemic vascular resistance, hypertension [1], atherogenic lipid profile, and coagulation abnormality [2].

Hypothyroidism was reported to be strongly related to cardiovascular disease, respiratory complications, neurological complications, and a significant difference in ventilator weaning time [3].

Severe thyroid dysfunction is related to muscle relaxation and lead to respiratory muscle depression and disturbed conscious level.[3]

Surgical stress of cardiac surgery might be followed by a prolonged recovery process and cardiac dysfunction [3].

The exact physiology of thyroid disease and the relationship with post cardiac surgery remain unclear. Thus far, large-scale clinical statistical analysis evidence on the complication rate and long-term mortality is lacking. Current important prognostic assessment tools such as EuroSCORE II [4], and Society of Thoracic Surgeons (STS) score [5] do not include thyroid function assessment, even though it has a significant impact on the metabolic, cardiovascular, and circulation system.

2. AIM/ OBJECTIVES (Maximum 300 words)

The primary aim of this study is to investigate the effect of supplementation of oral levothyroxine in delayed recovery patients post cardiac surgery.

3. METHODOLOGY:

Patients and Methods/ Subjects and Methods/ Material and Methods (Maximum 1000 words) "References may be needed"

This study is a prospective, randomized controlled trial that will study the postoperative clinical outcomes of levothyroxine supplementation in delayed recovery or prolonged ventilation patients post cardiac surgery.

Randomization will be performed using a computer-generated randomization sequence and allocation concealment to be maintained all through the time of procedure, by using opaque, numbered, and sealed envelopes.

The study protocol will receive ethical approval from the Research Ethical Committee/ Institutional Review Boards, Faculty of Medicine Ain Shams University.

Informed consent will be obtained from each patient before patients' allocation.

Type of the study: prospective randomized clinical trial study protocol.

Study Setting: The operating theaters and ICU of Cardiothoracic institute of Ain Shams University Hospitals.

Study period: one year.

Sample Size:

Using PASS 15 program for sample size calculation, setting power at 80% and alpha error at 0.05, it is estimated that sample size of 25 patients per group total 50 patients can detect an effect size .80 or the difference between two groups regarding different qualitative outcome measures using two-sized a z test

Study population:

Inclusion criteria:

- Age group: Adult patients from age of 45 to 70 years.

Hypothyroidism was reported to be strongly related to cardiovascular disease, respiratory complications, neurological complications, and a significant difference in ventilator weaning time [3].

- Sex: Both sexes
- Elective, urgent and emergency open heart surgeries.

Exclusion criteria:

- Patients refuse to give informed consent.
- Patient younger than 45 years old, older than 70 years old.

- Off pump patients.
- Patients known hypothyroidism on levothyroxine supplementation.
- Patients known hyperthyroidism on Carbimazole.

Sampling method:

Patients will be randomly allocated by computer generated randomization into two groups A and B:

- **Group A (Study group):** patients receiving oral supplementation of levothyroxine.
- **Group B (Control):** patients receiving Placebo drug.

Anesthetic management:

Full standard preoperative assessment for cardiac surgery will be done for all patients included in the study before planned procedures.

Premedication will be given according to standard protocol in cardiac anesthesia. Routine monitoring included a five-lead electrocardiogram, pulse oximeter and invasive blood pressure. Anesthesia will be induced with midazolam 0.02mg/kg and fentanyl 2-5 microgram /kg and muscle relaxation were achieved cisatracurium 0.15 mg/kg intravenous. After tracheal intubation, central venous line and TEE inserted, then anesthesia will be maintained throughout the procedure with morphin20 microgram/kg /min, cisatracurium 2mg/kg/min and sevoflurane 2%. Ventilation will be adjusted to maintain end-tidal carbon dioxide in the range of 30-40 mmHg.

On ICU arrival all patients will be subjected to standardized management as per institutional protocols. Patients who show signs of delayed recovery defined as either prolonged ventilation for 48 hours or delayed conscious level recovery for 48 hours despite exclusion of muscle relaxants and/or sedative drugs. Those patients will undergo CT brain, CT chest and neurological examination to exclude structural damage as per institutional protocols. Also, metabolic profile screening including full kidney function, full liver function, electrolyte and thyroid profile (TSH, free T3, free T4) to exclude correctable metabolic abnormalities.

Patients then divided into two groups: group A will receive levothyroxine via Ryle, dose of 25 to 50 ug/ day according to BMI, while group B will receive placebo in form of inert starch tablet.

Daily assessment of conscious level according to Glasgow Coma Scale (GCS) and spontaneous breathing trial by ICU consultant till ICU discharge.

Assessment of thyroid profile (free T3, free T4, TSH) before hospital discharge.

Endpoints of the study:

Primary end point:

1. Improvement of Glasgow coma scale and spontaneous breathing trial before ICU discharge.

Secondary end points:

1. Total ventilation time.
2. Total ICU stay.
3. Total hospital stay.
4. Total amount of inotropic support.
5. Improvement of cardiac function by echocardiography.

Ethical considerations:

The study protocol will receive ethical approval from the Research Ethical Committee, Faculty of Medicine Ain Shams University.

Informed consent will be obtained from each patient before patients' allocation.

Sample Size Calculation

Using PASS 15.0 (NCSS LLC), detecting an effect size of 0.80 in GCS change ($\alpha = 0.05$, power = 80%) required 25 patients per arm. To ensure adequate power for secondary endpoints and allow for dropouts, we enrolled 35 patients per group (total $n = 70$).

Statistical Analysis

Analyses adhered to the intention-to-treat principle. Continuous variables are reported as mean \pm SD or median (IQR) and compared using Student's t-test or Mann-Whitney U test, as appropriate. Categorical variables are expressed as counts (%) and compared by χ^2 or Fisher's exact test.

- **Primary analysis:** Linear mixed-effects regression modeled GCS trajectories over time, with group, time, and their interaction as fixed effects and patient as a random effect.
- **Time-to-event outcomes:** Kaplan-Meier curves and Cox proportional hazards models yielded hazard ratios (HRs) and 95% confidence intervals (CIs).
- **Mediation:** The Sobel test quantified the proportion of EF preservation attributable to changes in free T3.

- **Sensitivity and subgroup analyses:** Inverse probability weighting assessed robustness; prespecified subgroups included diabetes status and CPB duration > 200 minutes.

All tests were two-tailed with $\alpha < 0.05$. Statistical analyses were performed using R v4.3.1 with the lme4, lavaan, and survminer packages.

4. REFERENCES (Maximum 20 references)

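### The printed cisatracurium maintenance rate is 13.3 times the printed induction dose every minute; the magnitude is implausible and the line should be checked against the source and reconciled

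*Combined protocol and SAP*

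**What the plan says.** The Anesthetic management section of the combined protocol and SAP mentions cisatracurium twice, in consecutive sentences.

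- At induction: "muscle relaxation were achieved cisatracurium 0.15 mg/kg intravenous".
- After intubation and placement of the central line and echocardiography probe: "anesthesia will be maintained throughout the procedure with morphin20 microgram/kg /min, cisatracurium 2mg/kg/min and sevoflurane 2" percent.

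The same section leaves premedication to local routine ("Premedication will be given according to standard protocol in cardiac anesthesia") and later leaves ICU care and imaging to institutional protocols. It does not do so for maintenance of anaesthesia, where it prints its own drugs, numbers and units and applies them to the whole operation. No other section restates, limits or comments on the cisatracurium rate.

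Two further statements bear on the consequences. Allocation comes only after the 48-hour delayed-recovery criterion and the work-up ("Patients then divided into two groups"). The Sample Size Calculation section reports enrolment in the past tense ("we enrolled 35 patients per group").

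**The concern.** The first sentence treats 0.15 mg/kg as enough to produce relaxation, and by the order of the text that dose comes before intubation. The second sentence then gives many times that amount in every minute of the operation, with no explanation. A reader has no means of telling from the document whether the number, the unit or the time base is at fault.

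What is at stake is safety and the record. The maintenance line is worded as an instruction for study patients, in a public protocol. Following it literally would be a safety problem, and the line could be copied into later work. The statistical inference is not at stake, because the anaesthetic regimen is the same for everyone and precedes allocation.

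**Working it through.** The document derives neither figure, so there is no stated result to reproduce. The check is a direct comparison of the two printed numbers.

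**Inputs** (both from Anesthetic management)
- Induction dose: 0.15 mg/kg, given once.
- Maintenance rate: 2 mg/kg/min. The duration is the whole operation, and no number of minutes is given.

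**Step 1: ratio per minute.** Rate / dose = 2 / 0.15 = 13.33 induction doses per minute.

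**Step 2: time to repeat the induction dose.** Dose / rate = 0.15 / 2 = 0.075 min, and 0.075 × 60 = 4.5 seconds.

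**Step 3: one hour.** 2 × 60 = 120 mg/kg, and 120 / 0.15 = 800 induction doses.

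**Step 4: does body weight matter?** No. For a patient of weight w kg the ratio is (2 × w) / (0.15 × w) = 13.33, and w cancels. With assumed weights, for illustration:

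| Assumed weight | Induction dose | Maintenance per minute |
|---|---|---|
| 50 kg | 7.5 mg | 100 mg |
| 70 kg | 10.5 mg | 140 mg |
| 100 kg | 15 mg | 200 mg |

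**Step 5: a longer duration, as illustration only.** The Statistical Analysis section says "prespecified subgroups included diabetes status and CPB duration > 200 minutes". That is a subgroup cut-off for time on bypass, not an infusion time. Over 200 minutes the printed rate would give 2 × 200 = 400 mg/kg, and 400 / 0.15 = 2,667 induction doses (rounded). This restates the ratio in step 1 over a longer time and adds no separate evidence.

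**Step 6: does the text explain the gap?** It gives no cap, no total, no definition of the unit and no cross-reference to a maintenance protocol. In the same sentence the morphine rate is printed in micrograms and the cisatracurium rate in milligrams. That shows mixed notation, but not which entry, if any, is mistyped.

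**The case against.** The strongest objection is that a dose in mg/kg and a rate in mg/kg/min cannot contradict each other in the strict sense. The document does not say how maintenance should relate to induction, sets no maximum and reports no total that the rate would violate. This stands. A reader might infer that the protocol gives two conflicting values for one quantity, and it does not. What remains is a judgement of magnitude, but it can be made from the document's own sequence: a dose that is said to achieve relaxation is followed by the same amount every 4.5 seconds for the whole operation.

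A second objection is that the line may have been damaged in typing or in reading the PDF. The drug name and number before it are run together, and the spacing is irregular. This also stands as a possibility. It is neither shown nor excluded: microgram units are printed in plain letters elsewhere in the section, and Greek symbols survive in the Statistical Analysis section. It is the reason for checking the source first.

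A third objection is that anaesthetists would follow usual practice whatever the line says. That may prevent harm, but it does not correct the text.

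Two stronger readings are tempting and are not supported.

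- A reader might infer that patients were given the printed rate. Nothing in the documents shows this.
- A reader might infer that residual relaxant compromised eligibility, since entry depends on delayed recovery. The criterion already requires "delayed conscious level recovery for 48 hours despite exclusion of muscle relaxants and/or sedative drugs", at least for conscious level, and no delivered dose is documented. The anaesthetic text is also common to both groups, so it gives no ground for a claim of bias between arms.

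**Conclusion.** The point holds as an implausible figure that needs reconciling. As printed, maintenance delivers 13.3 induction doses of cisatracurium per minute, and no statement in the documents accounts for it. The ratio rests only on the two printed numbers and needs no assumption about weight or length of surgery. That the cause is an error of unit, symbol or time base is likely but is an inference. The documents do not show which figure or unit is wrong, or whether the error lies in the source or in the extracted text.

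The finding covers the cisatracurium figures only. Its effect on the between-arm comparison, sample size and power is nil. If enrolment is complete, as the past tense in the Sample Size Calculation section suggests, correction repairs the record and prevents reuse of the line; it would not protect patients already treated.

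**What to change.** Compare the maintenance sentence in Anesthetic management with the source file, looking at the number, the unit and the time base. If the source reads differently, the point closes. If it reads the same, the sponsor must reconcile the two cisatracurium statements and correct the protocol text. This review does not say which figure is right and proposes no dose.

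The cost is one check of the source and, if needed, a correction of one line. Design, data collection and analysis do not change.

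### Patients can enter on prolonged ventilation alone, with possibly little room to improve on GCS, yet the primary model and the 0.80 effect size use GCS alone and ignore entry route and baseline GCS

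*Combined protocol and SAP*

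**What the plan says.** All references are to the combined protocol and SAP.

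- **Entry.** Under Anesthetic management (section 3), a patient qualifies with "delayed recovery defined as either prolonged ventilation for 48 hours or delayed conscious level recovery for 48 hours". A qualifier on this rule sets drug causes aside: "despite exclusion of muscle relaxants and/or sedative drugs". The opening of section 3 describes the population in the same disjunctive way: "levothyroxine supplementation in delayed recovery or prolonged ventilation patients post cardiac surgery". Neither the inclusion nor the exclusion criteria set a GCS limit.
- **Primary endpoint.** "Improvement of Glasgow coma scale and spontaneous breathing trial before ICU discharge". No rule says how the two components combine.
- **Measurement.** "Daily assessment of conscious level according to Glasgow Coma Scale (GCS) and spontaneous breathing trial by ICU consultant till ICU discharge". No rule is given for the verbal item while a patient is intubated.
- **Sample size.** Sample Size Calculation refers to "detecting an effect size of 0.80 in GCS change", giving 25 per arm, raised to 35. It gives no source, mean difference, SD or reference population for the 0.80. The earlier sample size paragraph in section 3 attaches the same 0.80 to qualitative outcomes.
- **Primary analysis.** "Linear mixed-effects regression modeled GCS trajectories over time, with group, time, and their interaction as fixed effects and patient as a random effect". The breathing trial is not in this model. The analysis is by intention to treat.
- **Allocation and subgroups.** "Patients will be randomly allocated by computer generated randomization into two groups A and B", with no strata mentioned. The named subgroups are diabetes and bypass time above 200 minutes.

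**The concern.** The entry rule has two branches, and the primary analysis measures only one of them. Excluding relaxants and sedatives as the cause does not require reduced consciousness in a patient who qualifies by ventilation. A patient who is awake but not weaned is therefore eligible and may have little GCS to gain.

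Such patients affect the GCS comparison in two ways. They pull the average treatment difference towards zero. They also add variance, because the impaired patients tend to recover over time while these patients stay where they are. The model has no term that would absorb that variance.

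At stake are the power of the primary analysis and the reading of a null result, which could reflect case mix as much as absence of effect on consciousness. The breathing trial is the component most relevant to ventilation-only patients, and neither the primary model nor the sample size uses it.

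**Working it through.** **1. The plan's own figure.** Two-sided alpha 0.05, power 80%, effect 0.80:

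n = 2 × (1.960 + 0.842)² / 0.80² = 15.70 / 0.64 = 24.5, so 25 per arm.

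The t-test version gives 25.52, so 26 (power at 25 per arm is 79.1%). The stated 25 is reproduced. At 35 per arm with no dropout, power for 0.80 is 91%.

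**2. Adding patients without headroom.** The documents give neither of the following, so both are assumptions shown over a range:
- f, the share of patients whose GCS cannot change (change taken as exactly 0);
- m, the natural mean GCS gain of impaired controls, in units of their SD.

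Impaired controls have mean change m and impaired treated patients m + 0.80, each with SD 1. Then:
- all-patient difference = 0.80(1 − f);
- variance in an arm whose impaired patients have mean μ = (1 − f)(1 + fμ²);
- d = 0.80(1 − f) / √(average of the two arm variances).

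Example, f = 25% and m = 1: the control variance is 0.75 × 1.25 = 0.9375 and the treated variance is 0.75 × (1 + 0.25 × 1.8²) = 1.3575. The SD is √1.1475 = 1.071, so d = 0.60 / 1.071 = 0.56.

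Effect size d and two-sample t power at 35 per arm:

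| f | m = 0 | m = 1 | m = 2 |
|---|---|---|---|
| 10% | 0.75, 87% | 0.69, 81% | 0.60, 70% |
| 25% | 0.67, 79% | 0.56, 64% | 0.44, 44% |
| 50% | 0.53, 58% | 0.39, 37% | 0.28, 22% |

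Simulation of the same set-up agrees to about one percentage point (88% to 71%, 80% to 45% and 58% to 21%).

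**3. Where power falls below 80%.** If the SD is unchanged by the mix, d = 0.80(1 − f), and power at 35 per arm drops below 80% at f of about 15%. If patients without headroom have zero variance and the separation in means is ignored, d = 0.80√(1 − f), and the limit is about 28%. With a natural gain of 1 SD it comes sooner: 81% at f = 10% and about 75% at f = 15%.

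**4. Adjusting for entry route, all 70 patients kept.** This removes the between-route variance and leaves a residual SD of about √(1 − f). So d is about 0.80(1 − f) / √(1 − f) = 0.80√(1 − f): 0.69 at f = 25% and 0.57 at f = 50%. Power is about 80–82% and 60–65%, almost regardless of m. Restricting to impaired patients leaves 35 × 0.75 = 26.25 or 35 × 0.50 = 17.5 per arm, with power of 81% and 63%. The two approaches are equivalent in power.

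**5. Chance imbalance.** With a 50:50 mix and no strata, the arms differ in entry route by 7 of 35 (20 percentage points) or more in about 12% of trials. At f = 25% it is about 7%.

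All power figures are for a two-group comparison of change. The variance and correlation inputs needed for the planned mixed model are not given.

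**The case against.** **Patients on ventilation cannot improve on GCS.** A reader might infer this, but the documents do not say it. Baseline GCS is not stated, and ventilated patients may also have reduced consciousness. With no rule for the verbal item, an awake intubated patient may score below 15 and rise on extubation. That gain would reflect removal of the tube and not consciousness, so it does not rescue the endpoint. It does make zero change an assumption.

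**The analysis describes a different population from the one enrolled.** This too is not supported. The intention-to-treat comparison validly estimates the effect in the enrolled mix. The 0.80 is tied to no population and could have been meant for that mix. What can be said is that it is not justified for it.

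**The either/or rule has a rationale.** The introduction links thyroid dysfunction to both respiratory muscle weakness and disturbed consciousness, and the primary endpoint names the breathing trial. This stands as a defence of the entry rule. It does not defend a primary model that drops the breathing trial.

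**Chance imbalance in entry route is not bias.** This stands. The unadjusted standard error already contains it: simulated under no effect, with half the patients at ceiling and a 2 SD gain, the type I error was 5.5%. The cost is precision.

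**The loss may be small.** This stands as a possibility. With no natural gain and f = 25%, the unadjusted analysis has about 80% power against about 82% when restricted to impaired patients, so almost all the benefit of handling entry route comes from the assumed gain.

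**Conclusion.** The gap in the plan is certain and its size is not. The entry rule admits ventilation-only patients without a GCS limit, and neither the primary model, the allocation, the subgroups nor the effect size takes account of entry route or baseline GCS. Power at 35 per arm could be nearly intact (87% at 10% without headroom and no natural gain) or very low (22% at 50% and a 2 SD gain).

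These figures rest on an effect of 0.80 SD confined to impaired patients, zero change in the others, no dropout and a two-group comparison of change. If 0.80 is the effect in the whole enrolled mix, the stated power holds. The plan should say which it means. A change is worth making because adjustment costs little and protects against the unfavourable cases.

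**What to change.** 1. Record the entry criterion met and the GCS at allocation, and state how the verbal item is scored during intubation.
2. If allocation is not complete, randomise in two strata: impaired consciousness (with or without ventilation) and ventilation only. Stratify only together with item 3. Stratifying without adjusting gains nothing: at f = 50% and a 1 SD gain, power was 26% against 36% with neither.
3. Keep all 70 patients. Add entry route, its interaction with time, and baseline GCS to the primary GCS model. Restricting the primary set to impaired patients gives the same power but narrows the conclusion, so it is not needed.
4. Prespecify two supporting analyses: the GCS effect in patients impaired at allocation, and the breathing-trial result in patients ventilated at allocation. Both sets are defined by facts known before randomisation. State how the two components of the primary endpoint combine.
5. State the expected case mix, and that 80% power for 0.80 holds only if that effect applies to it.

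**Cost:** a protocol and SAP amendment, a second envelope set and a few model degrees of freedom, with no extra patients. Even so, power at f = 50% stays near 60–65%. Section 3 is written in the future tense, while Sample Size Calculation reports enrolment as done. If enrolment is complete, only the analysis changes are possible, and they should be labelled with their date.

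### The stated GCS model leaves out thyroid values measured before allocation; adding free T3 and TSH is a cheap, probably modest gain in precision, not a correction of bias

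*Combined protocol and SAP*

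**What the plan says.** The Introduction gives the clinical rationale: "Severe thyroid dysfunction is related to muscle relaxation and lead to respiratory muscle depression and disturbed conscious level". The aim is to "investigate the effect of supplementation of oral levothyroxine in delayed recovery patients post cardiac surgery", with no restriction by thyroid status.

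The last paragraphs under Anesthetic management describe the work-up of patients who meet the definition of delayed recovery. Imaging comes first: "Those patients will undergo CT brain, CT chest and neurological examination to exclude structural damage as per institutional protocols". Kidney, liver and electrolyte tests follow, with a "thyroid profile (TSH, free T3, free T4) to exclude correctable metabolic abnormalities". Allocation is described next: "Patients then divided into two groups". In the order of the text, then, the thyroid values precede allocation.

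Under Statistical Analysis, the primary analysis is a linear mixed model for GCS over time, "with group, time, and their interaction as fixed effects and patient as a random effect". The two subgroups named are diabetes and long bypass time. The one analysis that names a thyroid value is the mediation analysis, which relates change in free T3 to ejection fraction and not to GCS.

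The Exclusion criteria mention thyroid disease twice: "Patients known hypothyroidism on levothyroxine supplementation" and "Patients known hyperthyroidism on Carbimazole". They name no screening result.

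**The concern.** A baseline measurement that predicts the outcome can sharpen a randomised comparison at no cost in validity, and it corrects for chance differences between small arms. The plan collects such a measurement in every patient before allocation, and its own rationale gives a reason to expect that the measurement predicts conscious level, at least at the severe end. The stated GCS model does not use it. With 35 patients per arm, some precision may be given away, and a chance imbalance in thyroid status would go unadjusted in the primary result.

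A smaller matter of wording bears on how much adjustment can gain. Screening is done to exclude abnormalities, which may mean barring the patient or ruling out a cause. The exclusion list does not settle this. If abnormal results bar enrolment, the range of thyroid values among randomised patients is narrower and there is less for a covariate to explain.

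**Working it through.** **Inputs from the documents** (Sample Size Calculation; Statistical Analysis): effect size 0.80 in GCS change, alpha 0.05 two-sided, power 80%, 25 per arm required, 35 per arm enrolled.

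**Assumed:** the share of variance in GCS change explained by baseline free T3 and TSH together (R²). The documents give no figure, so 0, 0.05, 0.10 and 0.20 are shown. The mixed model is approximated by least squares on GCS change. Results at 25 per arm show the case in which the whole margin above 25 is lost.

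**1. The plan's own figure.** n per arm = 2(1.960 + 0.842)²/0.80² = 2 × 7.85/0.64 = 24.5, so 25. It reproduces. A t test gives 25.5, so 26. Unadjusted power by t test is 91.0% at 35 per arm and 79.1% at 25.

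**2. Variance after adjustment.** With two covariates and n per arm, the expected ratio of adjusted to unadjusted variance of the group difference is (1 - R²)(2n - 3)/(2n - 5). The first factor is the gain. The second is the price of estimating two extra slopes: 67/65 = 1.031 at 35 per arm and 47/45 = 1.044 at 25.

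| R² | ratio, 35 per arm | change | ratio, 25 per arm | change |
|---|---|---|---|---|
| 0 | 1.031 | +3% | 1.044 | +4% |
| 0.05 | 0.979 | -2% | 0.992 | -1% |
| 0.10 | 0.928 | -7% | 0.940 | -6% |
| 0.20 | 0.825 | -17% | 0.836 | -16% |

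A 20,000-run simulation at R² of 0, 0.10 and 0.20 gave ratios of 1.028, 0.930 and 0.827 at 35 per arm, and 1.041, 0.941 and 0.839 at 25. These agree with the formula.

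**3. Break-even.** The ratio equals 1 when R² = 2/(2n - 3). This is 2/67 = 0.030 at 35 per arm and 2/47 = 0.043 at 25.

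**4. Power for an effect of 0.80** (same simulation).

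| | unadjusted | R² = 0 | R² = 0.10 | R² = 0.20 |
|---|---|---|---|---|
| 35 per arm | 91% | 90.3% | 92.9% | 95.1% |
| 25 per arm | 79% | 77.9% | 81.4% | 85.6% |

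**5. Chance imbalance.** Suppose a share p of randomised patients has an abnormal thyroid result (p is assumed). Treating the counts in the two arms as independent binomials, the probability that the arms differ by 20 percentage points or more (7 patients of 35) is 7.2% for p = 0.25 and 12.0% for p = 0.50. At 25 per arm it is 14.0% and 20.3%.

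**6. Does the effect vary with free T3?** A group-by-free-T3 term was simulated with TSH in the model, residual SD 1 and an assumed correlation of -0.4 between the two values. Its 95% interval has a half-width of about 0.50 residual SD per SD of free T3 at 35 per arm, and 0.61 at 25. Power at 35 per arm for an interaction of 0.40 is 35%. Such a term could only be exploratory.

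**The case against.** The strongest reply is that adjustment is optional. The aim concerns delayed-recovery patients as a group, the unadjusted comparison answers it without bias, and power at 35 per arm is already 91%. With R² unknown, even the direction of the change in variance is not certain: below about 3% explained variance, adjustment costs a little. This stands, and it makes the point an improvement rather than an error.

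The premise is also narrower than it may look. The Introduction speaks of severe dysfunction, which does not establish a linear slope across the whole range of free T3 and TSH. It also calls the relation of thyroid disease to the course after cardiac surgery unsettled. This stands too, and it is why R² of 0 is in the range.

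A reader might infer that the plan rules out any use of baseline thyroid values. It does not. Inverse probability weighting is listed without its covariates, the subgroup list is not worded as complete, and the change in free T3 presumably uses the screening value. Only the absence of a stated use for GCS is supported.

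Finally, the Sample Size Calculation and Statistical Analysis sections are in the past tense, so the change may come too late to be prespecified. That limits its status, not its feasibility.

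**Conclusion.** The point holds as a low-cost improvement. Values measured before allocation, which the plan's rationale links to conscious level in severe dysfunction, have no stated role in the GCS analysis. Using them would change the variance of the group difference by between +3% and -17% at 35 per arm, and power from 91% to about 90-95%, for assumed R² from 0 to 0.20. These figures rest on that assumed range and on least squares for GCS change in place of the mixed model. The gain shrinks if abnormal thyroid results bar enrolment.

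Three stronger readings are not supported:

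- **Bias or a wrong sample size.** Randomisation protects the unadjusted comparison, and 25 per arm reproduces.
- **Low power because only patients with abnormal thyroid values can benefit.** The documents do not say this, and the aim is not restricted to such patients.
- **Thyroid-abnormal patients are definitely enrolled, or definitely barred.** The text allows both readings. The trial has one institute, and no inconsistent enrolment is documented. What remains is a wording gap between the exclusion list and the screening paragraph.

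**What to change.** **Model.** Add baseline free T3 and baseline TSH to the stated GCS mixed model as continuous covariates, each with its interaction with time. The time interactions matter because the treatment effect of interest is a difference in trajectory. State in advance the scale on which each value enters.

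**Status.** Make this the primary model only if nobody has seen outcomes by arm. Otherwise keep the stated model as primary and report the adjusted one beside it as a labelled post hoc sensitivity analysis.

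**Optional.** A free T3 interaction with treatment may be reported as an exploratory estimate with its 95% interval. No conclusion should depend on its significance.

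**Wording.** Reconcile the Exclusion criteria with the screening paragraph under Anesthetic management, so that both state the same consequence of an abnormal screening result. Which rule applies is for the sponsor.

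**Cost.** No new measurements are needed. With linear time the model gains four terms (two main effects and two time interactions); categorical time needs more. If the covariates predict nothing, the variance rises by about 3% at 35 per arm and 4% at 25.
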